Tolerability of therapy with Mexidol® and placebo was considered as satisfactory; 41 adverse events (AEs) were registered in 32 patients. There were 37 cases of AEs in 28 patients and 4 cases of severe AEs (SAEs). In the majority of cases the association of AE with the investigational products was determined as absent, in 3 cases - as possible. These abnormalities were random in nature and could develop, including against the background of the underlying and concomitant diseases. No deaths have been reported.

Thus, Mexidol® improves metabolism and blood supply to the brain, has hypolipidemic action, improves energy metabolism of the cell, affects the content of biogenic amines, inhibits free radical oxidation of lipids, increases the activity of antiradical defence enzymes. The result of realisation of the above properties is improvement of memory, learning, preservation of the memory trace and, as a consequence, counteraction to the process of fading of the instilled skills and reflexes, which ultimately contributes to the recovery of motor functions of stroke patients.

Further details of the experimental and clinical results are presented in the Investigator's Brochure.

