Interval (quantitative) data will be described using: arithmetic mean, standard deviation, median, lower (25%) and upper (75%) quartiles, minimum, maximum and coefficient of variation. Categorical (qualitative) data will be described using frequencies, percentages and/or fractions.

To compare quantitative data distributed according to the normal distribution law, it is planned to use standard parametric criteria: Student's t-test for dependent/independent samples, analysis of variance (ANOVA) for repeated measures.

It is planned to use standard nonparametric criteria to compare quantitative data distributed according to a law other than normal: Mann-Whitney U-test, Wilcoxon T-test, Friedman's criterion.

The test for conformity to the normal law of distribution will be carried out using the Shapiro-Wilk test.

Comparisons of frequencies of indicators between treatment groups will be made using Pearson's χ^2 test or Fisher's exact test.

9.7.3. Statistical methods for assessing the safety of using the investigational product and the comparator product

Safety parameters will be analysed in the ITT population.

Safety data will be analysed using the methods outlined for the application of the efficacy data assessment. Analyses of AEs will be performed based on an assessment of the incidence of adverse events / serious adverse events. Adverse events reported during the course of the trial will be presented by frequency (number of patients with AEs and number of such AEs in the group). AEs will also be presented by severity and relationship to investigational product

administration. Comparison of the number of patients with AE between therapy groups will be performed using Fisher's exact test or Pearson's χ^2 test.

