Secondary efficacy and safety endpoints and their changes will be presented using descriptive statistics by visit and therapy group. On trial visits, qualitative (dichotomous) measures will be compared between groups on the basis of Pearson's χ^2 test, if the frequency

Plan for statistical analysis of efficacy and safety parameters

of a feature in at least one subgroup is 5 or less, Fisher's exact test (or Fisher-Freeman-Galton test for tables of arbitrary dimensionality). Differences with p values of <0.05 will be considered statistically significant.

To compare quantitative data distributed according to the normal distribution law, it is planned to use standard parametric criteria: Student's t-test for dependent/independent samples, analysis of variance (ANOVA) for repeated measures.

It is planned to use standard nonparametric criteria to compare quantitative data distributed according to a law other than normal: Mann-Whitney U-test, Wilcoxon T-test, Friedman's test.

Benjamini-Yekuteli correction will be used for multiple statistical hypothesis testing.

A one-sided test will be applied to analyse the primary endpoint and two-sided statistical tests will be applied to analyse all secondary endpoints.

Scatter plots (boxplots) will be presented for all quantitative measures of efficacy and safety. Data whose distribution differs from normal at least at one visit in one of the groups will be presented as median and interquartile range; data whose distribution is normal at all visits will be presented as mean \pm standard deviation.

Pharmacodynamic effects will be analysed in a subpopulation of patients participating in the evaluation of the pharmacodynamic effects of the investigational therapy.

The resulting data will be analysed using the methods outlined for the application of the efficacy data assessment.

The p-level values <0.05 will be considered statistically significant.

The trial did not include interim statistical analyses.

The application of methods of statistical analysis of the obtained data will be determined by their nature, type and features of their distribution. The feasibility of using a number of statistical methods will be assessed after the completion of the data set, due to the unknown nature of their distribution, sample homogeneity, etc. During the course of the analysis, it is possible to expand the list of methods used if it is necessary for qualitative data processing.

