1. Mild - no symptoms or mild symptoms, only clinical or diagnostic follow-up is required; no intervention is indicated;
2. Moderate - only minimal, localised or non-invasive interventions are indicated; limitation of activities of daily living;

Version 1.0 of 12.11.2021

Plan for statistical analysis of efficacy and safety parameters

3. Severe - severe or clinically significant but not immediately life-threatening; hospitalisation or prolongation of hospitalisation is indicated; loss of ability to work; limitation of self-care in activities of daily living;
4. Life-threatening / Disability - life-threatening consequences, urgent intervention required;
5. Fatal - death associated with an undesirable event.

Determination of the relationship of AE to the investigational product:

The investigator should assess the association of the adverse event with the investigational product:

- No - clearly and unequivocally related to extraneous causes only, and does not meet the criteria for an unclassifiable, conditional, doubtful, possible, probable or certain relationship.
- Yes - there is a reliable temporal relationship with the use of the medicinal product.

Criteria:

- may have been caused by a clinical condition or external factors or other prescribed treatments;
- clear temporal relationship between discontinuation of the investigational product or dose reduction and improvement;
- resumes upon rechallenge;
- is consistent with the known nature of the response to the investigational product.

The degree of certainty of causality with the investigational product will be assessed using the WHO scale, taking into account the trial design (multiple administration):

Definite. Clinical manifestations of AEs, abnormalities of laboratory parameters occur during the period of drug administration, cannot be explained by the presence of existing diseases and the influence of other factors.

Probable. Clinical manifestations of AEs, abnormalities of laboratory parameters are related in time to the use of the drug, unlikely to be related to concomitant diseases or other factors.

Possible. Clinical manifestations of AEs, changes in laboratory parameters are related in time to the drug intake, but they can be explained by the presence of concomitant diseases or taking other drugs and the influence of chemical compounds.

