**Plan for statistical analysis of efficacy and safety parameters**

Table 21. Analysing the distribution of AEs by severity (template)

Severity		Investigational Product	
		Mexitol®	Placebo
Mild	Abs.		
	%		
Moderate	Abs.		
	%		
Severe	Abs.		
	%		
Life-threatening/ Disability to work	Abs.		
	%		
Fatal	Abs.		
	%		
Inter-group differences		Pearson 's χ^2 criterion or Fisher's exact test	p-value

Table 22. Relationship of AEs to investigational product (template)

The association of the adverse event with the investigational drug		Investigational Product	
		Mexitol®	Placebo
Yes	Abs.		
	%		
No	Abs.		
	%		
Differences between preparations		Pearson 's χ^2 criterion or Fisher's exact test	p-value

Table 23: Analysis of the distribution of AEs by administration of the Investigational Product (template)

Relationship to Investigational Product administration		Investigational Product	
		Mexitol®	Placebo
Definite.	Abs.		
	%		
Probable.	Abs.		
	%		
Possible.	Abs.		
	%		
Doubtful.	Abs.		

Version 1.0 of 12.11.2021

Protocol-Specific Version for Protocol #PHS-APIS-004-MEX-SOL-TAV. version 1.3 dated 07.06.2021

CONFIDENTIAL

page 51 of 58

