**Plan for statistical analysis of efficacy and safety parameters**

	%		
Conditional.	Abs.		
	%		
Unclassifiable.	Abs.		
	%		
Inter-group differences	Pearson 's χ^2 criterion or Fisher's exact test		p-value

Table 24. Analysis of the distribution of AEs by foreseeability (template)

Expectancy	Investigational Product		
	Mexitol®	Placebo	
Expected	Abs.		
	%		
Unexpected	Abs.		
	%		
Inter-group differences	Pearson 's χ^2 criterion or Fisher's exact test		p-value

Table 25. Analysis of AR distribution (template)

AE	Investigational Product		
	Mexitol®	Placebo	
AR	Abs.		
	%		
Not an AR	Abs.		
	%		
Inter-group differences	Pearson 's χ^2 criterion or Fisher's exact test		p-value

Table 26. Analysis of the distribution of AEs by seriousness (template)

Seriousness	Investigational Product		
	Mexitol®	Placebo	
Serious	Abs.		
	%		
Nonserious	Abs.		
	%		
Inter-group differences	Pearson 's χ^2 criterion or Fisher's exact test		p-value

Table 27. Analysing the distribution of AEs by actions taken (template)

Version 1.0 of 12.11.2021

Protocol-Specific Version for Protocol #PHS-
APIS-004-MEX-SOL-TAV. version 1.3 dated
07.06.2021

CONFIDENTIAL

page 52 of 58

Plan for statistical analysis of efficacy and safety parameters

Actions taken	Investigational Product	
	Mexidol®	Placebo
No action was taken	Abs.	
	%	
Other (specific actions taken will be indicated)	Abs.	
	%	
Inter-group differences	Pearson 's χ^2 criterion or Fisher's exact test	p-value

Table 28. Analysis of the distribution of AEs by outcome (template)

Outcome	Investigational Product	
	Mexidol®	Placebo
Transition to SAE	Abs.	
	%	
Stabilization of the condition (no change in condition):	Abs.	
	%	
Recovery with consequences	Abs.	
	%	
Recovery/termination of an AE without consequences:	Abs.	
	%	
Improved condition	Abs.	
	%	
Unknown:	Abs.	
	%	
Inter-group differences	Pearson 's χ^2 criterion or Fisher's exact test	p-value

Plan for statistical analysis of efficacy and safety parameters

Table 29. Summary table of the incidence of reported AEs in the group taking Mexidol by severity with randomization numbers of patients (N=) (template)

AE/code, PT according to MedDRA version	Mild AE		Medium AE		Moderate AE		Life-threatening AE		Fatal AE		Total		Total
	R	UR	R	UR	R	UR	R	UR	R	UR	R	UR	R+UR

Table 30. Summary table of the incidence of reported AEs in the group taking placebo by severity with randomization numbers of patients (N=) (template)

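### SAP Tables 21-28 appear to test counts of adverse events rather than patients: the p-values can be too small when events cluster, and the randomised denominator is lost

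*SAP*

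**What the plan says.** SAP section 13 contains eight templates that classify AEs: severity (Table 21, "Analysing the distribution of AEs by severity (template"), relationship (22 and 23), foreseeability (24), AR status (25), seriousness (Table 26, "Analysis of the distribution of AEs by seriousness (template"), action taken (27) and outcome (28). Each has Abs. and % rows per arm and closes with an inter-group p-value from a Pearson "criterion or Fisher's exact test". None states whether the rows count events or patients.

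Elsewhere the unit is the patient. Protocol 9.7.3: "Comparison of the number of patients with AE between therapy groups will be performed using Fisher's exact test" (or Pearson's test). SAP section 10 tabulates the number and proportion of patients with AEs, and puts severity, action and outcome under descriptive statistics. SAP section 3 says no departures from the protocol's analyses are planned.

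The general threshold, in SAP section 9, is: "The p-level values <0.05 will be considered statistically significant". Section 10 calls for Fisher's test when a frequency is 5 or less.

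On severity, section 10 defines five grades, the third being "Severe - severe or clinically significant but not immediately life-threatening". Tables 29, 30, 34 and 35 head their five severity columns Mild, Medium, Moderate, Life-threatening and Fatal.

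**The concern.** Two separate problems follow if the rows hold event counts.

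First, Pearson's and Fisher's tests treat every counted unit as independent. A patient with three AEs contributes three entries, and AEs in one patient tend to resemble each other in severity, attributed cause or outcome. The effective sample is then smaller than the table suggests, and the p-value is too small.

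Second, a comparison among events alone asks whether the mix of AEs differs between arms, not whether more randomised patients had a severe or serious one. Doubling every kind of AE leaves the mix unchanged. Conversely, fewer mild AEs in one arm raises that arm's share of severe AEs with no more severe events.

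The mislabelled headers are a smaller matter. Taken literally, they would print grade 3 events, including serious ones, under a heading that means grade 2.

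**Working it through.** **Step 1: which unit?** Table 19 separates total AEs from the number of patients with AEs, and Table 20 names patients explicitly, so the SAP says patients when it means patients. Tables 21-28 are framed in terms of AEs, list event attributes and have no row for patients without an AE. Event counts are therefore the natural reading, though an inferred one. Even a patient count in this layout would leave out patients without an AE.

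**Step 2: inputs.**
- From the documents: 304 randomised 1:1, so 152 per arm; nominal level 0.05. For EPICA, "41 adverse events (AEs) were registered in 32 patients", giving 41/32 = 1.28 AEs per affected patient, and 32/150 = 21.3% of the safety set affected.
- Assumed: a two-sided test (SAP section 9 says "two-sided statistical tests will be applied to analyse all secondary endpoints" and gives no separate rule for safety); the within-patient correlation ρ, shown from 0 to 1; the share of events in the category tested (10% or 40%); and, for a heavier load, 2 AEs per affected patient.

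The plan states no error rate for these tables beyond the nominal 5%, so it has no figure to reproduce.

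**Step 3: approximation.** With m events per affected patient and m_w = E[m²]/E[m], the variance is inflated by D = 1 + (m_w − 1)ρ, and the true two-sided size is about 2[1 − Φ(1.96/√D)].
- One AE per patient: m_w = 1, D = 1, size 5% at any ρ.
- m = 1 + Poisson(0.28): E[m²] = 0.28 + 1.28² = 1.92, m_w = 1.92/1.28 = 1.50. At ρ = 0.5, D = 1.25 and size is 8.0%. At ρ = 1, D = 1.50 and size is 11.0%.
- m = 1 + Poisson(1): E[m²] = 1 + 4 = 5, m_w = 5/2 = 2.5. At ρ = 0.5, D = 1.75 and size is 13.8%. At ρ = 1, D = 2.5 and size is 21.5%.
- ρ = 0: D = 1, no inflation.

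**Step 4: simulation under the SAP's test rule** (2×2 tables, no treatment effect, Fisher when a cell is 5 or less).

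| AEs per affected patient | Category share | ρ = 0 | ρ = 0.5 | ρ = 1 |
|---|---|---|---|---|
| 1.28 (EPICA) | 10% | 2.8% | 5.0% | 8.2% |
| 1.28 (EPICA) | 40% | 5.5% | 8.3% | 11.3% |
| 2 (assumed) | 10% or 40% | no inflation | about 12% upward | up to about 23% |

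With exactly one AE per patient the size was 3.1-5.3%. A more dispersed (geometric) event count, with 40% of patients affected and 2 AEs each, gave 16-17% at ρ = 0.5 and 25-27% at ρ = 1, so the spread of events matters as well as the mean. Testing patients with at least one event in the category, 152 against 152, gave at most 5.9%.

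**Step 5: the denominator.** Illustration with one AE per affected patient, so clustering plays no part: 30 severe and 30 non-severe AEs on the investigational product, 15 and 15 on placebo.
- Mix of events: 30/60 against 15/30, both 50%, p = 1.
- Patients: 30/152 = 19.7% against 15/152 = 9.9%. The pooled proportion is 45/304 = 0.148, SE = √(0.148 × 0.852 × 2/152) = 0.0407, z = 0.0987/0.0407 = 2.42, p = 0.015 (Fisher 0.023).

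**Step 6: headers.** Tables 29, 30, 34 and 35 have five columns for five grades in order. Medium and Moderate name the same level and no column is headed Severe, so the third label is wrong.

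**The case against.** The strongest reply has five parts.

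- **The unit is never written.** Protocol 9.7.3 and SAP section 10 both point to patients, so the analyst might count patients. This stands as a limit on certainty, but the layout points the other way and the texts still need reconciling.
- **Inflation is not general.** A reader might infer that these tests always exceed 5%. The documents do not support that: they give no within-patient correlation, and EPICA's load is light. EPICA's rarer categories were 4/41 = 9.8% severe or serious and 3/41 = 7.3% possibly related. At its load Fisher's test would apply in 93-99% of runs, with size 2.3-2.8% at ρ = 0, 4.4-4.5% at ρ = 0.5 and 5.8-6.9% only at ρ = 1. This stands. However, Protocol 8.3 classes newly detected or worsened abnormalities as AEs, so several per patient are plausible here.
- **Patient-level comparisons exist.** Table 20 compares patients with any AE and gives a relative risk; Tables 31 and 36 compare incidence by preferred term. In the Step 5 example Table 20 would show the overall excess (60/152 against 30/152). This stands, but none of these compares patients with at least one severe, related or serious AE overall.
- **No decision rule uses these p-values,** and the primary test is untouched. This stands. The safety conclusion nevertheless follows a statistical evaluation of all AEs, to which these tables contribute.
- **The headers are a slip.** A reader might infer that grade 3 has been dropped. It has not: Severe is a row in Table 21 and is defined in section 10, and severity is listed per event in Tables 32 and 37.

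The Benjamini-Yekutieli correction named in SAP section 9 does not answer the point: it adjusts for multiplicity and cannot repair p-values computed from dependent counts.

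**Conclusion.** The point holds in conditional form. As laid out, Tables 21-28 most naturally test event counts, which conflicts with Protocol 9.7.3 and, for severity, action and outcome, with SAP section 10. The size of the error depends on two things the documents do not give: AEs per affected patient in this trial and their within-patient correlation. It ranges from none, through a few points at EPICA's load, to a true size of about 12-23% at an assumed 2 AEs per affected patient with correlation 0.5-1. The lost denominator needs no such assumption: at any correlation the tables do not answer whether more randomised patients had a severe, related or serious AE. The severity headers need a label correction only. This should be settled before database lock; it affects safety reporting, not the primary efficacy conclusion.

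**What to change.** 1. State the counting unit in every AE template.
2. For severity, relationship, AR status and seriousness (Tables 21-23, 25 and 26), count each patient once, either as having at least one event in the category or at worst grade or closest relationship. Use the ITT safety population named in Protocol 9.7.3 and SAP section 11 as denominator, with patients without such an event shown. Apply Fisher's or the chi-square test and report the risk difference with a 95% CI.
3. Show event counts beside these without p-values.
4. Keep Tables 24, 27 and 28 descriptive. Foreseeability is assessed only for adverse reactions, and action and outcome (which includes unknown) have no natural worst category.
5. Head the severity columns of Tables 29, 30, 34 and 35 Mild, Moderate, Severe, Life-threatening and Fatal, as in SAP section 10.

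The cost is an SAP revision to the templates and a little programming. No new data, extra patients or change to the primary analysis is needed.

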**Plan for statistical analysis of efficacy and safety parameters**

	%		
Conditional.	Abs.		
	%		
Unclassifiable.	Abs.		
	%		
Inter-group differences	Pearson 's χ^2 criterion or Fisher's exact test		p-value

Table 24. Analysis of the distribution of AEs by foreseeability (template)

Expectancy	Investigational Product		
	Mexitol®	Placebo	
Expected	Abs.		
	%		
Unexpected	Abs.		
	%		
Inter-group differences	Pearson 's χ^2 criterion or Fisher's exact test		p-value

Table 25. Analysis of AR distribution (template)

AE	Investigational Product		
	Mexitol®	Placebo	
AR	Abs.		
	%		
Not an AR	Abs.		
	%		
Inter-group differences	Pearson 's χ^2 criterion or Fisher's exact test		p-value

Table 26. Analysis of the distribution of AEs by seriousness (template)

Seriousness	Investigational Product		
	Mexitol®	Placebo	
Serious	Abs.		
	%		
Nonserious	Abs.		
	%		
Inter-group differences	Pearson 's χ^2 criterion or Fisher's exact test		p-value

Table 27. Analysing the distribution of AEs by actions taken (template)

Version 1.0 of 12.11.2021

Protocol-Specific Version for Protocol #PHS-
APIS-004-MEX-SOL-TAV. version 1.3 dated
07.06.2021

CONFIDENTIAL

page 52 of 58

Plan for statistical analysis of efficacy and safety parameters

Actions taken	Investigational Product	
	Mexidol®	Placebo
No action was taken	Abs.	
	%	
Other (specific actions taken will be indicated)	Abs.	
	%	
Inter-group differences	Pearson 's χ^2 criterion or Fisher's exact test	p-value

Table 28. Analysis of the distribution of AEs by outcome (template)

Outcome	Investigational Product	
	Mexidol®	Placebo
Transition to SAE	Abs.	
	%	
Stabilization of the condition (no change in condition):	Abs.	
	%	
Recovery with consequences	Abs.	
	%	
Recovery/termination of an AE without consequences:	Abs.	
	%	
Improved condition	Abs.	
	%	
Unknown:	Abs.	
	%	
Inter-group differences	Pearson 's χ^2 criterion or Fisher's exact test	p-value

Plan for statistical analysis of efficacy and safety parameters

Table 29. Summary table of the incidence of reported AEs in the group taking Mexidol by severity with randomization numbers of patients (N=) (template)

AE/code, PT according to MedDRA version	Mild AE		Medium AE		Moderate AE		Life-threatening AE		Fatal AE		Total		Total
	R	UR	R	UR	R	UR	R	UR	R	UR	R	UR	R+UR

Table 30. Summary table of the incidence of reported AEs in the group taking placebo by severity with randomization numbers of patients (N=) (template)

Adverse event/code, PT level according to MedDRA version	Mild AE		Medium AE		Moderate AE		Life-threatening AE		Fatal AE		Total		Total
	R	UR	R	UR	R	UR	R	UR	R	UR	R	UR	R+UR

Table 31. Summary table of the incidence of AEs after taking each Investigational Product (template)

Adverse event/code, PT level according to MedDRA version	Mexidol N=		Placebo N=		P-value (Statistical criterion)
	n	%	n	%	

Version 1.0 of 12.11.2021

Protocol-Specific Version for Protocol #PHS-APIS-004-MEX-SOL-TAV.
version 1.3 dated 07.06.2021

CONFIDENTIAL

page 54 of 58

Plan for statistical analysis of efficacy and safety parameters

Table 32. List of all adverse events for each patient (template)

Site number	Randomization number, full name	Demographic data	AE/code, PT according to MedDRA version	AE onset	Severity	Seriousness	Relationship	Actions taken in relation to the patient	Actions taken in relation to the investigational product	Concomitant therapy	Date the AE resolved	Outcome
		Age, years										
		gender										
		Weight, kg										
		Height, cm										
		race										

Table 33. MedDRA version classification of AEs (template)

Randomization number, initials	AE	MedDRA AE code, SOC level	MedDRA AE term, SOC level	MedDRA AE code, PT level	MedDRA AE term, PT level

Version 1.0 of 12.11.2021

Protocol-Specific Version for Protocol #PHS-APIS-004-MEX-SOL-TAV.
version 1.3 dated 07.06.2021

CONFIDENTIAL

page 55 of 58

Plan for statistical analysis of efficacy and safety parameters

Table 34. Summary table of the incidence of reported SAEs in the group taking Mexidol by severity with randomization numbers of patients (N=) (template)

Adverse event/code, PT level according to MedDRA version	Mild AE		Medium AE		Moderate AE		Life-threatening AE		Fatal AE		Total		Total
	R	UR	R	UR	R	UR	R	UR	R	UR	R	UR	R+UR

Table 35. Summary table of the incidence of reported SAEs in the placebo group by grade with randomization numbers of patients (N=) (template)

Adverse event/code, PT level according to MedDRA version	Mild AE		Medium AE		Moderate AE		Life-threatening AE		Fatal AE		Total		Total
	R	UR	R	UR	R	UR	R	UR	R	UR	R	UR	R+UR

Table 36. Summary table of the incidence of SAEs after taking each investigational product (template)

Version 1.0 of 12.11.2021

Protocol-Specific Version for Protocol #PHS-APIS-004-MEX-SOL-TAV.
version 1.3 dated 07.06.2021

CONFIDENTIAL

page 56 of 58

Plan for statistical analysis of efficacy and safety parameters

Adverse event/code, PT level according to MedDRA version	Mexidol®		Placebo		P-value (Statistical criterion)
	N=	N	n	%	

Table 37. List of all serious adverse events for each patient (template)

Site number	Randomization number, full name	Demographic data	SAE/code, PT according to MedDRA version	AE onset	Severity	Seriousness	Relationship	Actions taken in relation to the patient	Actions taken in relation to the investigational product	Concomitant therapy	Date the AE resolved	Outcome
		Age, years										
		gender										
		Weight, kg										
		Height, cm										
		race										

Table 38. MedDRA version classification of SAEs (template)

Version 1.0 of 12.11.2021

Protocol-Specific Version for Protocol #PHS-APIS-004-MEX-SOL-TAV.
version 1.3 dated 07.06.2021

CONFIDENTIAL

page 57 of 58

Plan for statistical analysis of efficacy and safety parameters

Randomization number, initials	SAE	SAE MedDRA code, SOC level	SAE MedDRA term, SOC level	SAE MedDRA code, PT level	SAE MedDRA term, PT level

Version 1.0 of 12.11.2021

Protocol-Specific Version for Protocol #PHS-APIS-004-MEX-SOL-TAV.
version 1.3 dated 07.06.2021

CONFIDENTIAL

page 58 of 58
